## Précis:

**Objective:** The sensory basis of non-painful deep pressure sensation is not known. We recently found that innocuous pressure sensation is eliminated in rare sensory neuronopathy patients with a specific loss of A-beta fibers, strongly suggesting that A-beta fibers underlie the ability to sense deep pressure. In addition, we and others have shown that deep pressure touch (observed in hugs and massage) frequently conveys a sense of pleasantness. The current study aims to examine the role of A-beta fibers in the perception of deep pressure touch including both its intensity and the pleasant affect it often elicits. This study constitutes the second study of the K99 phase of a K99/R00 grant application awarded to [name] by NCCIH.

**Study Population:** Up to 24 healthy participants will be enrolled in the study with a goal of 12 completers. Participants will be invited based on previous screening and participation in our studies.

**Design:** Participants will undergo an ischemic-compression block. Sensory stimuli will be administered at frequent intervals to capture the loss of sensation related to A fibers as the block progresses. Before and after A-beta-associated sensations have been lost, the perception of deep pressure will be tested. Participants will rate the intensity and pleasantness of the pressure. Ratings of pain and discomfort will be collected throughout the study session.

**Outcome measures:** Primary outcome; Rating of intensity of deep pressure on the blocked arm before versus after loss of A-beta sensation, compared to ratings on the unblocked arm.

Secondary outcomes: 1) Rating of pleasantness of deep pressure on the blocked arm after loss of A-beta sensation, compared to ratings on the unblocked arm; 2) Ratings of intensity and pleasantness of gentle brushing on the blocked arm after loss of A-beta sensation, compared to ratings on the unblocked arm.

Precis posted online at [clinicaltrials.gov](https://clinicaltrials.gov): see Attachment 2

## List of Abbreviations

BP = Blood Pressure  
C-LTMR = C Low Threshold Mechanoreceptors  
CRIS = Clinical Research Information System  
DEC = Deputy Ethics Counselor  
DIR = Division of Intramural Research  
DoH = Declaration of Helsinki  
FWA = Federal Wide Assurance  
GUID = Global Unique Identifier  
HRPP = Human Research Protection Program  
Hz = Hertz  
INCF = International Neuroinformatics Coordinating Facility  
IRB = Institutional Review Board  
iRIS = Integrated Research Information System  
IRTA = Intramural Research Training Award  
LHP = Licensed Healthcare Practitioner  
mmHg = Millimeter of Mercury  
NCCIH = National Center for Complementary and Integrative Health  
NIDAG = Neuroimaging Data Access Group  
NIH = National Institutes of Health  
NINR = National Institute of Nursing Research  
NITRC = Neuroimaging Informatics Tools and Resources Clearinghouse  
NRS = Numeric Ratings Scale  
NSAIDs = Nonsteroidal Anti-Inflammatory Drugs  
OHSRP = Office for Human Subjects Research Protections  
PAIN = Pain and Interoception Imaging Network  
PI = Principal Investigator  
QA = Quality Assurance  
SAE = Serious Adverse Event  
SOP = Standard Operating Procedure  
SPSS = Statistical Package for the Social Sciences  
UP = Unanticipated Problem  
VAS = Visual Analogue Scale  
XNAT = eXtensible Neuroimaging Archive Toolkit

## 1. Introduction and Background

Deep pressure is a critical component of many touch therapies including massage therapy. However, the sensory basis of non-painful deep pressure perception is not known. A better understanding of the mechanism of deep pressure sensation in humans is important for understanding the mechanisms of manual therapies, as well as for

understanding pain-related changes in deep muscle sensation in individuals with chronic pain. Here, we investigate the role of myelinated (A) and unmyelinated (C) sensory afferents in the perception of deep pressure sensation. We hypothesize that A-beta fibers underlie both the intensity and pleasantness of innocuous deep pressure sensation.

Myelinated and unmyelinated sensory afferents innervate not only the epidermis but also muscle and connective tissues, and even bones [1, 2]. Numerous studies have shown the existence of unmyelinated muscle afferents with nociceptive properties, but little is known about sensations associated with the other afferent types innervating deeper tissues [3]. However, there is evidence that sensations of deep pressure also involve activation of sensory afferents below the level of the epidermis. Pressure-sensitive afferents have been reported in the skeletal muscle and tendon of cats [4], and in humans, anesthetizing the skin has shown deep pressure sensation to predominantly originate from deeper tissues below the skin [3]. However, it is not yet known whether deep pressure is perceived in these deeper tissues (muscle and/or connective tissues) by A or C fibers (or a mix). We tested patients with sensory neuropathy earlier this year and found that two (of two) patients lacking A-beta afferents were unable to perceive deep pressure at non-painful levels (Case & [name] et. al., manuscript under review). We therefore hypothesize that A-beta fibers underlie the perceived intensity of non-painful deep pressure.

An ischemic nerve block typically causes some discomfort and/or pain due to the high intensity of cuff pressure. Pain and discomfort are typically focused at the site of the inflated cuff. Healthy adult participants are typically able to tolerate at least a half hour of nerve block, but some discontinue testing between 30-60 minutes due to pain or discomfort [13]). Feelings of anxiety and disgust are also common due to the loss of sensation from the arm. Testing of pleasant sensation may be affected by the painful context of the nerve block. Pleasant sensations may be more difficult to detect or perceive during the experience of pain or other aversive affective states. However, pleasant sensations still occur and can be quantified during painful experiences. For example, patients with chronic pain still rate C-LTMR touch as significantly pleasant [15]. Since all ratings will be compared between arms, the painful context will affect the two arms equally and thus should not affect any positive conclusions drawn from our outcome measures.

Elucidating the sensory mechanisms of non-painful deep pressure will help us understand how manual therapies create calming and pleasant sensations and understand more about the analgesic effects of deep pressure. This could help to strengthen therapeutic strategies for treatment of chronic pain.

## 2. Study Objectives

### a. Primary objective:

**Hypothesis:** Participants will experience a significant decrease in the intensity of deep pressure after loss of A-beta-associated sensation due to ischemic-compression block.

### b. Secondary objectives:

**Hypothesis 1:** Participants will experience a significant decrease in the pleasantness of deep pressure after loss of A-beta-associated sensation due to ischemic-compression block.

**Hypothesis 2:** Participants will experience a significant decrease in the intensity *but not* pleasantness of gentle brushing after loss of A-beta-associated sensation due to ischemic-compression block.

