### **Details of Sensory testing paradigm**

Ratings of intensity and pleasantness of pressure and brushing: At baseline and after loss of sensation associated with A fibers, perception of deep pressure and gentle brushing will be tested on both arms. Deep pressure will be administered to the hand and wrist for approximately 20 seconds using a hand massager that applies oscillating pressure. Gentle brushing will be administered to the hand/forearm by a trained experimenter at a rate of approximately 3cm/second for approximately 15 seconds. Participants will rate intensity and pleasantness of each sensation on VAS scales with anchors of “no sensation” to “highest possible intensity” and from “extremely unpleasant” to “neutral” (midpoint) to “extremely pleasant.” Nearly identical VAS scales have been successfully used in our lab in numerous previous studies to distinguish the intensity versus pleasantness of sensory stimuli (e.g. [16, 17]). If cool perception is lost after light touch (not concurrently), A-delta fibers may be isolated and ratings can be collected again. Loss of cool and light touch often coincide, however [14]. Ratings of bad mood and anxiety will also be collected. They will be rated verbally on 0-10 scales (0 = none; 10 = worst you have experienced).

After placement of the tourniquet but before elimination of A-beta associated sensation, sensory testing will be conducted to monitor the block progression. Sensory testing will be conducted nearly continuously, which each test conducted approximately every ~1-2 minutes. All testing will be conducted distal to the block. The tests conducted during sensory monitoring may include the following:

Vibration perception (A-beta): A custom vibration device administering ~200 Hz vibration to the skin of the palm will be set for a random duration between 1-6 seconds. Participants will press a button (or similar response) when they perceive the onset and offset of the vibration.

Warm (C-fiber) and cool (A-delta) perception: Heat stimuli will be administered by the trained experimenter to the ventral surface of the forearm or palm using a contact

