## 10. Statistical Analysis

### a. Analysis of data/ study outcomes

#### Testing for normal distribution

All data will be assessed for normality of distribution using the Shapiro Wilk W test. A significant W statistic indicates that the hypothesis of a normal distribution should be rejected, i.e. a significant W indicates skewed data. If the data is skewed the data transformation method will be chosen based on the distribution (Box-Cox method) of the dependent variable. The resulting transformed data will be analyzed with parametric statistics. In the descriptions below we will describe the parametric statistical tests. If data transformation does not work, non-parametric tests will be applied.

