#### Behavioral Data

All behavioral data will be analyzed using SPSS or similar statistical package. A significance level of  $p < 0.05$  will be adopted for all analyses.

For the primary and secondary outcomes, we will use paired t-test or equivalent nonparametric test to evaluate the effect of the nerve block

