### b. Power analysis

In order to yield meaningful statistical analyses of the psychophysical data, and specifically for our primary outcome measure, we estimate that the sample size required to complete the study would be 12 healthy participants. G\*Power (<http://www.gpower.hhu.de>) was used to compute the necessary sample size. In our recent study of deep pressure perception (manuscript in preparation; data available upon request), the same oscillating deep pressure sequence was rated as an intensity  $M = 4.2$  (scaled to our 0-10 scale); we expect intensity to drop at least 2 points on our 0-10 rating scale (likely more since patients lacking A-beta fibers had no perception of deep pressure in our previous study, Case & [name] et. al., under review). In our previous study healthy participants rated the same deep pressure sequence on two different days and the standard deviation of the change in their rating from Day 1 to Day 2 was 1.7. Based on a

2-point change (due to blocking A-beta fibers which should fully eliminate sensation) and a standard deviation for within-subject rating change scores of 1.7, we expect a Cohen's effect size  $d = 1.17$ . Setting statistical power to 95% and Type I error probability to  $\alpha=0.05$ , 12 subjects would be required to complete the study. We expect up to a 50% dropout rate of participants based on prior NIH studies and the discomfort of prolonged nerve blocks found in other studies [13]. Thus, we will enroll up to 24 participants and dropouts will be replaced.

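### Hypothesis 2 predicts no significant fall in brushing pleasantness, but apart from a significant rise only a non-significant test can support it

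*Combined protocol and SAP*

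**What the plan says.** Section 2b, Hypothesis 2, has two parts: it predicts a significant "decrease in the intensity *but not* pleasantness of gentle brushing" once A-beta sensation is lost. The first part predicts a difference. The second predicts that a difference will not be found.

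Section 10a (Behavioral Data) gives one method for all primary and secondary outcomes: "we will use paired t-test or equivalent nonparametric test to evaluate the effect of the nerve block". The 0.05 significance level "will be adopted for all analyses"; whether tests are one- or two-sided is not stated. Section 10a (Testing for normal distribution) allows a Box-Cox transformation if data are skewed, after which "The resulting transformed data will be analyzed with parametric statistics", or a nonparametric test if transformation fails. No estimate on the VAS itself is promised.

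Section 9 defines the brushing outcomes as changes or differences relative to the unaffected arm. Section 4d describes the pleasantness VAS as bipolar, with neutral at its midpoint. Section 10b computes power only for deep-pressure intensity. Sections 9 and 10 give no equivalence or non-inferiority test, margin, confidence-interval rule or rule for an inconclusive result.

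**The concern.** A difference test on brushing pleasantness can end in three ways. A significant fall contradicts the prediction, and a significant rise is consistent with it. The third outcome is non-significance, which is what the hypothesis expects. Non-significance occurs when pleasantness is unchanged, but also when it falls and 12 people are too few to show it. The plan has no means of telling these apart.

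The incentive also runs the wrong way. If there is a real fall, noisier ratings make apparent support for the hypothesis more likely.

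This half of the hypothesis matters scientifically. Section 1 describes C low-threshold mechanoreceptors as afferents for pleasant slow stroking, and brushing pleasantness that survives A-beta loss is the result that would fit that account. Under the plan as written, a small null result could be reported as that finding.

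**Working it through.** **Inputs.** From section 10b: 12 completers, power 95%, alpha 0.05, an expected change of 2 points, and "a standard deviation for within-subject rating change scores of 1.7". That SD is for deep-pressure intensity rated on two days. The documents give no SD for brushing pleasantness, so the main calculation is in SD units and needs neither an assumed SD nor a scale coding. It assumes normally distributed paired differences.

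**The plan's own figure.** d = 2/1.7 = 1.176. For a paired t-test, power comes from the noncentral t distribution with n − 1 degrees of freedom and noncentrality d√n.
- Two-sided 0.05: n = 12 gives 95.9%, n = 11 gives 93.9%. The required n is 12, as stated.
- One-sided 0.05: the required n is 10.
- Enrolment: 12/(1 − 0.5) = 24, as stated.

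The sample size for the primary outcome reproduces, and it implies a two-sided test. Two-sided results are therefore the main ones below.

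**Precision at n = 12.** The 95% half-width is t(0.975, 11)/√12 = 2.201/3.464 = 0.635 SD.

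**Probability of a non-significant result.** With T a noncentral t (11 df, noncentrality d√12), this is P(−2.201 < T < 2.201) for the two-sided test:

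| True fall (SD units) | d√12 | Two-sided | One-sided 0.05 |
|---|---|---|---|
| 0 | 0 | 95% | 95% |
| 0.5 | 1.732 | 65% | 51% |
| 0.8 | 2.771 | 29% | 17% |
| 1.0 | 3.464 | 12% | 6% |

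The first row does not depend on the SD: with no true change, the test is non-significant 95% of the time however noisy the ratings.

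**Illustration in points (assumptions).** Suppose 0–10 coding, and suppose the SD of 1.7 applied to the change in each arm. The SD of the between-arm difference in change is then 1.7 × √(2(1 − ρ)), where ρ is the correlation between the two arms' changes.

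| ρ | SD of difference | 95% half-width = 0.635 × SD | 1-point fall non-significant, two-sided | One-sided |
|---|---|---|---|---|
| 0.75 | 1.20 | 0.76 | 25% | 15% |
| 0.5 | 1.70 | 1.08 | 54% | 40% |
| 0 | 2.40 | 1.53 | 74% | 62% |

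The same 1-point fall goes from usually detected to usually missed as noise increases, and each miss would count as support for the hypothesis.

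**What a margin could achieve.** Take a 1-point margin (assumed) and no true change. The probability that the one-sided 95% lower bound lies above −1 is P(T > 1.796), with noncentrality (1/SD) × √12. It is 85%, 60% or 38% at SDs of 1.20, 1.70 or 2.40.

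**The case against.** The strongest reply is that the hypothesis only says there will be no significant decrease, and the planned test checks exactly that. The documents never claim equivalence, nor do they say that non-significance will be treated as proof. Section 1 defends only positive conclusions against the painful context of the block. This is true, and it limits the charge: the plan does not announce a faulty inference. But a prediction about a p-value that imprecision helps to fulfil is not a useful test of preserved pleasantness, and the plan offers no other way to judge it.

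A second point is that 12 completers are not uninformative. A fall of 1.0 SD would be detected 88% of the time, and one of the size planned for pressure intensity (1.176 SD) would be missed only about 4% of the time. That stands. Non-significance carries some evidence against a large fall; the gap concerns moderate ones.

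Third, the points illustration borrows an SD from another stimulus and another rating, and the Précis can be read as a post-block comparison where section 9 uses changes. Both are fair. The SD-unit figures need no borrowed SD and hold for whichever paired difference is analysed.

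Finally, a direct test that intensity falls more than pleasantness would avoid relying on a null result. It would be a reasonable addition, but it would not itself show that pleasantness is unchanged.

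**Conclusion.** The concern holds. Apart from a significant rise, the only support the plan allows for the pleasantness half of Hypothesis 2 is a non-significant difference test in 12 people. Such a test misses a true fall of 0.5 SD in 65% of trials and of 0.8 SD in 29%, assuming a two-sided test and normal differences; one-sided testing gives 51% and 17%. The results in points depend on an assumed SD and coding, and serve only to show the range.

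This should be fixed, because following the plan as written lets an imprecise null count as support for a named hypothesis. The defect is confined to that half of one secondary hypothesis. The primary outcome, Hypothesis 1 and the brushing-intensity prediction are ordinary difference hypotheses and are unaffected.

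**What to change.** Add the following to section 10a, before data collection:

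1. A non-significant test will not be taken as evidence that brushing pleasantness is preserved.
2. The between-arm difference in change will be reported with its 95% confidence interval on the original VAS, whatever the normality check leads to. Use a t interval if the untransformed t-test is used; otherwise use the Hodges-Lehmann estimate with its signed-rank interval, noting that this estimates a pseudomedian and not a mean.
3. The pleasantness half of Hypothesis 2 is descriptive.

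Only if a margin can be justified on the bipolar VAS and fixed in advance should the plan allow a conclusion of preservation. It would be drawn when the one-sided 95% lower bound lies above minus that margin; otherwise the result would be inconclusive. The documents give no basis for a margin, so the descriptive label is the default.

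The cost is a few sentences, with no new data and no extra participants. The downside is that this half may end without a firm conclusion. The margin route does not reliably remove that risk, given the 38% to 85% success rates above for a 1-point margin.

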## 3. Subjects

### a. Description of study populations

Based on our power calculations, we would like to have 12 healthy men and women who meet the inclusion/exclusion criteria described below participate in the study. Because of possible dropouts during the study due to discomfort of the nerve block, we will set our maximum accrual at 24 participants (see detailed explanation of sample size estimate on p. 21). Withdrawals/dropouts will be replaced. In accordance with HRPP SOP 14F and provided they are not subordinates, relatives, or co-workers of the investigators, or NCCIH DIR employees, NIH employees may participate in this study.

### b. Inclusion criteria

All subjects must be:

1. Between 18 and 50 years old.
2. Fluent in English.

3. Able to provide written informed consent.
4. Enrolled in 16-AT-0077, "Clinical and Scientific Assessment of Pain and Painful Disorders"

**c. Exclusion criteria**

1. Unable to comply with study procedures.
2. Have used recreational drugs in the past 30 days.
3. Pregnancy or breastfeeding.
4. Congenital upper limb deficiency or amputation.
5. Peripheral neuropathy, dermatological condition such as scars or burns, or has had a tattoo in the testing region within the previous four weeks that might influence cutaneous sensibility.
6. Current chronic pain condition or has had chronic pain in the past year (painful condition lasting more than six months), including ongoing treatment with medications for neuropathic pain (e.g. gabapentin, tricyclic antidepressants, pregabalin, tramadol).
7. Major medical condition, such as kidney, liver, cardiovascular (including blood clots, hypertension, preexisting cardiac arrhythmia, lymphadenopathy), autonomic, pulmonary, or neurological problems (e.g., seizure disorder) or a chronic systemic disease (e.g., diabetes) or Raynaud's disease.
8. Personal history or first-degree family history of blood clots or clotting and circulatory disorders
9. History of a seizures or first-degree family member with a seizure disorder
10. High ( $>140/90$ ) or low ( $<90/60$ ) blood pressure
11. Current and untreated diagnosis of major depression, post-traumatic stress syndrome, bipolar disorder, psychosis, anxiety or panic disorder, alcohol or substance use disorders
12. History of fainting with blood draws
13. Any medical counter-indications to the nerve blocks.
14. Participant's arm unable to fit in inflated arm blood pressure cuff

15. Participant has taken any pain medication other than an over-the-counter NSAIDs or acetaminophen within the last month or for more than one month on a continual basis within last six months.
16. Used topical pain-relieving creams in the testing area within 24 hours of testing or non-steroidal anti-inflammatory drugs (NSAIDS), (e.g. aspirin, ibuprofen, acetaminophen, or naproxen) within 3 days of testing
17. Recent use of medications that increase risk of seizures (e.g. antidepressant Wellbutrin or antipsychotic Haldol)
18. NIH employees who are subordinates, relatives, or co-workers of the investigators, or NCCIH DIR employees.

#### **Exclusion criteria for individual study session**

1. Shows signs of alcohol withdrawal syndrome, or has behavioral signs of intoxication: will be excluded immediately and not have the possibility to reschedule their session.
2. Used topical pain-relieving creams in the testing area (e.g. methylsalicylate, capsaicin) within 24 hours of testing or used non-steroidal anti-inflammatory drugs (NSAIDS, e.g. aspirin, ibuprofen), acetaminophen, or naproxen within 3 days of testing. \*

\* To be determined during the pre-session screening (see Attachment 1: Pre-Session Screening). Participants who cannot refrain from these activities may have their session rescheduled up to two times. If the participant is found non-compliant during the second rescheduled appointment, he or she will be excluded from the study.

An Eligibility Checklist can be found in Attachment 1.

